**Table 3: Study Arms and Dose Levels**

Vaccination Group	Group Name	Composition	Total Dose	N (total)
1	mRNA-1011.1	A/H1N1, B/Yamagata, B/Victoria, A/H3N2 (Darwin), A/H3N2 (Newcastle) at 1:1:1:1:1	50 µg	100
2	mRNA-1011.2	A/H1N1, B/Victoria, A/H3N2 (Darwin), A/H3N2 (Newcastle) at 1:1:1:1	40 µg	100
3	mRNA-1012.1	A/H1N1, B/Victoria, A/H3N2 (Darwin), A/H3N2 (Newcastle), A/H3N2 (Hong Kong) at 1:1:1:1:1	50 µg	100
4	mRNA-1012.1	A/H1N1, B/Victoria, A/H3N2 (Darwin), A/H3N2 (Newcastle), A/H3N2 (Hong Kong) at 1:1:1:1:1	62.5 µg	100
5	mRNA-1010 (Darwin) (Control)	A/H1N1, B/Yamagata, B/Victoria, A/H3N2 (Darwin) at 1:1:1:1	50 µg	100
6	mRNA-1010.2 (Newcastle) (Control)	A/H1N1, B/Yamagata, B/Victoria, A/H3N2 (Newcastle) at 1:1:1:1	50 µg	100
7	mRNA-1010.3 (Hong Kong) (Control)	A/H1N1, B/Yamagata, B/Victoria, A/H3N2 (Hong Kong) at 1:1:1:1	50 µg	100

Abbreviations: mRNA = messenger ribonucleic acid.

## 4.2. Scientific Rationale for Study Design

This study will enroll healthy adults aged  $\geq 50$  to  $\leq 75$  years to evaluate next-generation influenza mRNA vaccine candidates. This broad age range allows inclusion of older adults who often have higher risk of comorbidities and conditions that could lead to more negative health outcomes due to influenza. mRNA-1011.1, mRNA-1011.2, and mRNA-1012.1 could provide a public health benefit through increasing protection against circulating influenza A/H3N2 strains.

The additional H3N2 strains evaluated in this study were selected by the Sponsor for their antigenic distance compared to the Darwin strain contained in the 2022/2023 NH vaccine composition and greater antigenic breadth across the H3N2 virus family. Due to WHO reporting

limited circulation of the B/Yamagata virus in recent years, the mRNA-1011.1 and mRNA-1012.1 candidates were designed to not contain the B/Yamagata HA, allowing for higher proportion of other strains/additional strains to be represented in the vaccine. Data from this study will help distinguish the immune responses against the respective vaccine strains, using the HAI assay, and evaluate the added benefit of mRNAs encoding additional influenza A/H3N2 strains from the WHO recommended strains. The Sponsor expects to follow public health recommendations for inclusion of multiple H3N2 strains once such recommendations are available.

The study will be conducted in an open-label manner. Since all study arms will receive DP in a relatively narrow dosage range that have the same clinical indication, developed with the same technology platform (mRNA platform) and there is no placebo arm, the preference or bias for particular study products would be perceived to be minimum from either investigators' or participants' perspective.

#### **4.3. Justification for Dose**

The selection of the 50- $\mu$ g dose level of the Sponsor's mRNA-1010 candidate is supported by the data from the Phase 1/2 and the Phase 2 NH interim analyses (see mRNA-1010 IB).

The safety and immunogenicity profile observed from the mRNA-1010-P101 study supports the use of 50  $\mu$ g total mRNA dose level as the dose to base a dose-ranging study of these next-generation influenza mRNA candidates and in the selection of dosage of control comparisons. mRNA-1010 is a quadrivalent vaccine and contains 12.5  $\mu$ g of mRNA encoding for each HA strain for a total of 50  $\mu$ g mRNA, the dose of all the mRNA-1010 controls.

The mRNA-1011.1 and mRNA 1011.2 each contain 10  $\mu$ g of each HA strain, resulting in a 50  $\mu$ g and 40  $\mu$ g dosage in the pentavalent and quadrivalent vaccine, respectively. mRNA-1012.1 is also a pentavalent vaccine and has a total dose of 50  $\mu$ g with 10  $\mu$ g of each HA. Lastly, mRNA-1012.1 will also be tested at a 62.5  $\mu$ g dose, with 12.5  $\mu$ g of each HA strain similar to the mRNA-1010 controls, thereby allowing evaluation of reactogenicity of each HA strain at the same dosage.

#### **4.4. End of Study Definition**

A participant is considered to have completed the study if he or she has completed all periods of the study ([Table 1](#)). The end of study is defined as completion of the last visit of the last participant in the study or last scheduled procedure(s) as shown in the SoE ([Table 1](#)).

## 5. STUDY POPULATION

Prospective approval of protocol deviations to recruitment and enrollment criteria, also known as protocol waivers or exemptions, is not permitted.

### 5.1. Inclusion Criteria

Each participant must meet all of the following criteria to be enrolled in this study:

1. Adults  $\geq 50$  to  $\leq 75$  years of age at the time of consent (Screening Visit) who, in the opinion of the Investigator, are in good health based on review of medical history and physical examination performed at the Screening Visit.
2. Investigator assessment that participant understands and is willing and physically able to comply with protocol-mandated follow-up and procedures.
3. Able to provide written informed consent for participation in this study, including all evaluations and procedures as specified in this protocol.
4. Body mass index of  $18 \text{ kg/m}^2$  to  $35 \text{ kg/m}^2$  (inclusive) at the Screening Visit.
5. Women of nonchildbearing potential may be enrolled in the study. Nonchildbearing potential is defined as postmenopausal or permanently sterilized. FSH level may be measured at the discretion of the Investigator to confirm postmenopausal status.
6. Women of childbearing potential may be enrolled in the study if the participant fulfills all the following criteria:
  - Has a negative pregnancy test at the Screening Visit and on the day of vaccination (Day 1).
  - Has practiced adequate contraception or has abstained from all activities that could result in pregnancy for at least 28 days prior to Day 1. Adequate female contraception is defined as consistent and correct use of a locally authorized or approved contraceptive method in accordance with the product label.
  - Has agreed to continue adequate contraception through 3 months following vaccine administration.
  - Is not currently breastfeeding.

### 5.2. Exclusion Criteria

Participants meeting any of the following criteria will be excluded from the study:

1. Acutely ill or febrile (temperature  $\geq 38.0^{\circ}\text{C}/100.4^{\circ}\text{F}$ ) 72 hours prior to or at the Screening Visit or Day 1. Participants meeting this criterion may be rescheduled within the 28-day screening window and will retain their initially assigned participant number.
2. Clinical screening laboratory values for total white blood cell count, hemoglobin, alanine aminotransferase, aspartate aminotransferase, creatinine, alkaline phosphatase, and total bilirubin are  $>\text{Grade 1}$  or platelets  $\geq\text{Grade 1}$ .

3. History of a diagnosis or condition that, in the judgment of the Investigator, is clinically unstable or may affect participant safety, assessment of safety endpoints, assessment of immune response or adherence to study procedures.
  - Asymptomatic conditions and conditions with no clinically significant end-organ involvement (eg, mild hypertension, dyslipidemia) are not exclusionary, provided that the participant is being appropriately managed and are clinically stable (ie, unlikely to result in symptomatic illness within the time course of this study). Illnesses or conditions may be exclusionary, even if otherwise stable, due to therapies used to treat them (eg, immunosuppressive treatments), at the discretion of the Investigator.
  - Participants who have undergone surgical procedures within 28 days prior to Day 1 or are scheduled to undergo a surgical procedure within 28 days after study intervention administration are excluded. Minor surgical procedures under local anesthesia (eg, excision of skin lesion) or screening and diagnostic procedures (eg, colonoscopy) are allowed.
4. Reported history of congenital or acquired immunodeficiency, immunocompromising/immunosuppressive condition, asplenia, or recurrent severe infections. The following conditions are permitted at the discretion of the Investigator:
  - Certain immune-mediated conditions that are stable and well controlled (eg, Hashimoto thyroiditis), as well as those that do not require systemic immunosuppressants (eg, asthma, psoriasis, or vitiligo) may be permitted at the discretion of the Investigator.
5. Dermatologic conditions that could affect local solicited AR assessments (eg, tattoos, psoriatic patches or vitiligo affecting skin over the deltoid injection site area).
6. History of anaphylaxis or severe hypersensitivity reaction requiring medical intervention after receipt of a vaccine or any of the components contained in mRNA vaccines.
7. Coagulopathy or a bleeding disorder that is considered a contraindication to IM injection or phlebotomy.
8. Diagnosis of malignancy within previous 5 years (excluding non-melanoma skin cancer).
9. Any medical, psychiatric, or occupational condition, including reported history of substance abuse, that in the opinion of the Investigator might pose additional risk due to participation in the study or could interfere with the interpretation of study results.
10. Has received systemic immunosuppressants for >14 days in total within 180 days prior to the Randomization Visit (for glucocorticosteroids  $\geq 10$  mg/day of prednisone or equivalent) or is anticipating the need for systemic immunosuppressive treatment at any time during participation in the study (including intra-articular steroid injections). Inhaled, nasal, and topical steroids are allowed.
11. Has received or plans to receive any licensed or authorized vaccine, including COVID-19 vaccines,  $\leq 28$  days prior to the study injection (Day 1) or plans to receive a licensed or authorized vaccine within 28 days after the study injection.
12. Has received a seasonal influenza vaccine or any other investigational influenza vaccine within 180 days prior to the Randomization Visit.

13. Has tested positive for influenza by local health authority-approved testing methods within 180 days prior to the Randomization Visit.
14. Has been treated with antiviral therapies for influenza (eg, Tamiflu®) within 180 days prior to the Randomization Visit.
15. Has had close contact with someone with laboratory-confirmed influenza infection or with someone who has been treated with antiviral therapies for influenza (eg, Tamiflu) within the past 5 days prior to the Randomization Visit.
16. Has had close contact to someone or been diagnosed themselves with respiratory syncytial virus or SARS-CoV-2 infection as defined by the CDC in the past 10 days prior to the Randomization Visit.
17. Has received systemic immunoglobulins, long-acting biological therapies that affect immune responses (eg, infliximab), or blood products within 90 days prior to the Randomization Visit or plans to receive them during the study.
18. History of myocarditis, pericarditis, or myopericarditis.
19. History of Guillain-Barre syndrome.
20. Has donated  $\geq 450$  mL of blood products within 28 days prior to the Randomization Visit or plans to donate blood products during the study.
21. Has participated in an interventional clinical study within 28 days prior to the Randomization Visit or plans to do so while participating in this study. Participants may continue in prior interventional study follow-up activities, as long as it does not involve further investigational treatment other than described in this protocol. (Note: Interventions such as counseling, biofeedback, and cognitive therapy are not exclusionary).
22. Is working or has worked as a study personnel or is an immediate family member or house member of study personnel, study site staff, or Sponsor personnel.

### **5.3. Lifestyle Restrictions**

Participants must not eat or drink anything hot or cold within 10 minutes before oral temperature is taken. Participants should defer vaccination with licensed or authorized vaccines, including COVID-19 vaccines, until after completion of their Day 29 Visit.

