**Table 2: Study Objectives and Endpoints**

Objectives	Endpoints
Primary	

 
To evaluate the safety and reactogenicity of mRNA-1011.1, mRNA-1011.2, mRNA-1012.1, and mRNA-1010 controls (mRNA-1010, mRNA-1010.2 and mRNA-1010.3)
 
	
 
Solicited local and systemic ARs through 7 days after injection
 
Unsolicited AEs through 28 days after injection
 
MAAEs from Day 1 to Day 181/EoS
 
AESIs from Day 1 to Day 181/EoS
 
SAEs from Day 1 to Day 181/EoS
 
AEs leading to discontinuation from Day 1 to Day 181/EoS
 

Secondary	

 
To evaluate the humoral immunogenicity of mRNA-1011.1, mRNA-1011.2, mRNA-1012.1 in comparison with mRNA-1010 controls (mRNA-1010, mRNA-1010.2, and mRNA-1010.3) against vaccine-matched influenza A and B strains at Day 29
 
	
 
GMT and GMFR, comparing Day 29 with Day 1 (baseline), and percentage of participants with seroconversion, defined as a postbaseline titer <math>\geq 1:40</math> if baseline is <math>< 1:10</math> or a 4-fold or greater rise if baseline is <math>\geq 1:10</math> in anti-HA antibodies measured by HAI assay
 

Exploratory (may be performed)	

 
To evaluate the humoral immunogenicity of mRNA-1011.1, mRNA-1011.2, mRNA-1012.1, and mRNA-1010 controls against vaccine-matched influenza A and B strains at all evaluable humoral immunogenicity timepoints
 
	
 
GMT, GMTR (mRNA-1011.1, mRNA-1011.2, and mRNA-1012.1 against mRNA-1010), and GMFR (compared with Day 1) of anti-HA as measured by HAI assay
 

 
To evaluate the humoral immunogenicity against vaccine-matched influenza A and B strains by alternative methods at all evaluable timepoints
 
	
 
GMT and GMFR (compared with Day 1) of anti-HA antibodies as measured by MN assays or other alternative methods against vaccine matched strains
 

 
To evaluate the humoral immunogenicity against vaccine-mismatched influenza A and B strains at all evaluable timepoints
 
	
 
GMT and GMFR (compared with Day 1) of anti-HA antibodies as measured by HAI or MN assays against vaccine-mismatched strains
 

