### **6.7.3. Concomitant Medications and Vaccines that May Lead to the Elimination of a Participant from Per-Protocol Analyses**

The use of the following concomitant medications and/or vaccines will not require withdrawal of the participant from the study but may determine a participant's evaluability in the PP analysis (Analysis sets are described in [Section 9.4.](#)):

- Any investigational or non-registered product (drug or vaccine) other than the study intervention used during the study period.
- Immunosuppressants administered chronically (more than 14 days in total) during the study period. For corticosteroids,  $\geq 10$  mg/day of prednisone or equivalent is not permitted. Inhaled, nasal, and topical steroids are allowed.
- An authorized or licensed vaccine administered within 28 days after the study vaccination.
- Immunoglobulins or long-acting biological therapies that affect immune responses (eg, infliximab) or any blood products administered during the study period.

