**Table 9: Analysis Sets**

Set	Description
Randomization Set	The randomization set consists of all participants who are randomly assigned.
FAS a	The FAS consists of all randomly assigned participants who receive the study vaccination.
PP Set b	The PP Set consists of all participants in the FAS who comply with the injection schedule, comply with the timings of immunogenicity blood sampling to have a baseline and at least the Day 29 post-injection assessment, have no RT-PCR-confirmed influenza infection prior to Day 29 visit and have no major protocol deviations that impact the immune response.
Safety Set c	The safety set consists of all randomly assigned participants who receive the study vaccination.
Solicited Safety Set d	The solicited safety set consists of all participants in the safety set who contribute any solicited AR data.

Abbreviations: AR = adverse reaction; FAS = full analysis set; PP = per-protocol; RT-PCR = reverse transcriptase polymerase chain reaction.

- a For the FAS, participants will be analyzed according to the group to which they were randomized.
- b The PP Set will be used as the primary analysis set for analyses of immunogenicity unless otherwise specified. Participants will be analyzed according to the group to which they were randomized.
- c The safety set will be used for all analyses of safety, except for the solicited ARs. Participants will be included in the vaccination group corresponding to what they actually received.
- d The solicited safety set will be used for the analyses of solicited ARs, and participants will be included in the vaccination group corresponding to what they actually received.

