5.3. Per-Protocol Set

The Per-Protocol (PP) Set consists of all participants in the FAS who comply with the injection schedule, comply with the timings of immunogenicity blood sampling to have a baseline and at least the Day 29 post-injection assessment (-7 / +14 days of Day 29), have no RT-PCR-confirmed influenza infection prior to Day 29 visit (Day 29 immunogenicity

assessment+7 days) and have no major protocol deviations that impact the immune response. The PP Set will be used as the primary analysis set for analyses of immunogenicity unless otherwise specified. Participants will be analyzed according to the group to which they were randomized.

Participants with a dosing error will be considered as having a protocol deviation. However, the determination of whether to include/exclude participants from the PP Set due to dosing error will be based on the dosage difference (in μg) between the actual dose received and the randomized dose. The PP Set exclusion criteria for participants with dosing error are described in [Table 3](#).

Table 3: PP Set Exclusion Criteria for Dosing Errors

Group Name	Exclusion Conditions
mRNA-1011.1 50 μg	Any mRNA-1011.2 received, any mRNA-1012.1 received, any mRNA-1010 (Darwin) (Control) received, any mRNA-1010.2 (Newcastle) (Control) received, any mRNA-1010.3 (Hong Kong) (Control) received, mRNA-1011.1 received $\leq 37.5 \mu\text{g}$, or mRNA-1011.1 received $> 75 \mu\text{g}$
mRNA-1011.2 40 μg	Any mRNA-1011.1 received, any mRNA-1012.1 received, any mRNA-1010 (Darwin) (Control) received, any mRNA-1010.2 (Newcastle) (Control) received, any mRNA-1010.3 (Hong Kong) (Control) received, mRNA-1011.2 received $\leq 30 \mu\text{g}$, or mRNA-1011.2 received $> 60 \mu\text{g}$
mRNA-1012.1 50 μg	Any mRNA-1011.1 received, any mRNA-1011.2 received, any mRNA-1010 (Darwin) (Control) received, any mRNA-1010.2 (Newcastle) (Control) received, any mRNA-1010.3 (Hong Kong) (Control) received, mRNA-1012.1 received $\leq 37.5 \mu\text{g}$, or mRNA-1012.1 received $> 56.25 \mu\text{g}$
mRNA-1012.1 62.5 μg	Any mRNA-1011.1 received, any mRNA-1011.2 received, any mRNA-1010 (Darwin) (Control) received, any mRNA-1010.2 (Newcastle) (Control) received, any mRNA-1010.3 (Hong Kong) (Control) received, mRNA-1012.1 received $\leq 56.25 \mu\text{g}$, or mRNA-1012.1 received $> 93.75 \mu\text{g}$

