- Up to 28 days following vaccination: starts from the day of vaccination (Day 1) and 27 subsequent days, or up to the study discontinuation or death, whichever comes earlier. This analysis period will be used as the primary analysis period for safety analyses including unsolicited AEs, except for solicited ARs, unless specified otherwise.

Study day relative to the injection will be calculated as below:

- a) Study day prior to the injection will be calculated as: date of assessment/event – date of the injection, and
- b) Study day on or after the date of the injection will be calculated as: date of assessment/event – date of the injection + 1.

Incomplete/missing data will be handled as follows:

- Imputation rules for missing prior/concomitant medications, non-study vaccinations and procedures are provided in [Appendix B](#).
- Imputation rules for missing AE dates are provided in [Appendix C](#).
- If laboratory results (including antibody values) are reported as below the lower limit of quantification (LLOQ) (e.g., <0.1), the numeric values will be imputed by $0.5 \times$ LLOQ in the summary. If laboratory results (including antibody values) are reported as greater than the upper limit of quantification (ULOQ) (e.g., >3000), the numeric values will be imputed by ULOQ in the summary if actual values are not available.
- Other incomplete/missing data will not be imputed, unless specified otherwise.

- A row denoted “Missing” will be included in count tabulations where specified on the shells to account for dropouts and missing values.

Vaccination groups to be used for summary purposes:

- mRNA-1010 50 µg
- mRNA-1010.2 50 µg
- mRNA-1010.3 50 µg
- mRNA-1011.1 50 µg
- mRNA-1011.2 40 µg
- mRNA-1012.1 50 µg
- mRNA-1012.1 62.5 µg
- All (the combined group will be applicable to the disposition and baseline demographics only)

6.2. **Background Characteristics**

6.2.1. **Participant Disposition**

The number and percentage of participants in the following categories will be summarized by vaccination group based on the Randomization Set:

- Randomization Set
- FAS
- PP Set
- Safety Set
- Solicited Safety Set

Percentages will be based on the number of participants in the vaccination group within the Randomization Set. For the Solicited Safety Set, the percentages will be based on the number of participants in the vaccination group within the Safety Set (as treated). The number of participants in the Safety Set (as treated) will be provided.

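### The deferral of other vaccines ends at a visit allowed from Day 22, so it can lapse inside the Day 1–28 primary unsolicited-AE period

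*Protocol*

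**What the plan says.** Protocol Section 5.3 ties the end of the deferral to an event: "Participants should defer vaccination with licensed or authorized vaccines, including COVID-19 vaccines, until after completion of their Day 29 Visit". It sets no minimum number of days. Table 1 gives the Day 29 Visit a window of -7/+3 days. The SAP uses the same lower limit for the PP Set, requiring "at least the Day 29 post-injection assessment (-7 / +14 days of Day 29", so a Day 22 visit is both compliant and evaluable.

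Three other provisions bear on vaccines in this interval:

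- Exclusion criterion 11 (Section 5.2) removes anyone who "plans to receive a licensed or authorized vaccine within 28 days after the study injection".
- Section 6.7.3 lists a licensed or authorized vaccine given in the 28 days after study vaccination among items whose use "will not require withdrawal of the participant from the study but may determine" evaluability in the PP analysis.
- Table 9 requires PP participants to "have no major protocol deviations that impact the immune response".

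On the safety side, Table 2 makes "Unsolicited AEs through 28 days after injection" a primary endpoint. Section 8.2.7 counts this as the vaccination day plus 27 more days. SAP Section 6.1 defines the same period, which "starts from the day of vaccination (Day 1) and 27 subsequent days, or up to the study discontinuation or death, whichever comes earlier", and adds: "This analysis period will be used as the primary analysis period for safety analyses including unsolicited AEs".

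**The concern.** The deferral and the AE period run on different clocks. The AE period is fixed at Days 1–28, while the deferral ends whenever the participant's own Day 29 Visit is done, possibly a week before the AE period closes. An event that follows another vaccine in that gap would count in the all-cause 28-day tables, because the AE definition in Section 8.4.2 does not depend on relatedness. SAP Section 6.1 shortens the period only for study discontinuation or death, not for another vaccine.

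The protocol is also at odds with itself. Criterion 11 and Section 6.7.3 both use 28 days after the injection, and only 5.3 uses a movable visit. A participant can follow 5.3 exactly and still receive a vaccine that 6.7.3 names as a possible reason for PP elimination.

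The 28-day safety data feed the interim analysis of a study meant to support choice of a lead candidate, so avoidable contamination of that window is worth closing if it is cheap to do so.

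**Working it through.** The plan gives no figure for this overlap, so there is none to reproduce. The check is day arithmetic.

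**Inputs**
- Day 29 Visit window: -7/+3 (Protocol Table 1).
- AE period: Day 1 plus 27 days (Protocol 8.2.7; SAP 6.1).
- Study day = date − injection date + 1 (SAP 6.1).
- Arm size: about 100 (Protocol Table 3).

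**Step 1. Visit window.** 29 − 7 = Day 22 and 29 + 3 = Day 32, so there are 11 allowed days.

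**Step 2. AE period.** 1 + 27 = Day 28, so the period is Days 1–28.

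**Step 3. The 28-day interval in 6.7.3.** Counted as elapsed days, injection date + 28 is study Day 28 + 1 = Day 29.

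**Step 4. Exposed days for a visit on day d**, counting the visit day itself because a vaccine could be given once the visit is completed:
- within Days 1–28: max(0, 28 − d + 1)
- within 28 elapsed days: max(0, 29 − d + 1)

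| Visit day | Exposed days, Day 1–28 period | Exposed days, 28 elapsed days |
|---|---|---|
| 22 | 7 | 8 |
| 23 | 6 | 7 |
| 24 | 5 | 6 |
| 25 | 4 | 5 |
| 26 | 3 | 4 |
| 27 | 2 | 3 |
| 28 | 1 | 2 |
| 29 | 0 | 1 |
| 30–32 | 0 | 0 |

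**Step 5. Average exposure.** The documents give no distribution of visit days. The average lies between 0 days (all visits on Day 29 or later) and 7 days (all on Day 22). If each of the 11 days were equally likely, which is an assumption, it would be (7+6+5+4+3+2+1)/11 = 28/11 = 2.5 days.

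**Step 6. Effect of one case.** One affected participant with no other unsolicited AE moves an arm of 100 by 1/100 = 1.0 percentage point.

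**Step 7. Would the event be recorded?** After an early visit the next scheduled contact is the Day 57 call, at 57 ± 5 = Days 52–62. The documents point both ways:
- For capture: the call script in Section 8.2.4 covers AEs and non-study vaccinations, and Section 8.2.7 has staff ask about changes in well-being at every contact.
- Against: Table 1 marks unsolicited-AE recording only at Visits 1 to 4 and unscheduled visits, and footnote l confines the calls to SAEs, MAAEs, AESIs and AEs leading to discontinuation.

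The clearest path into the 28-day tables is therefore through one of those four event types or an unscheduled visit.

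**Step 8. Floors compared.** A floor of study Day 29 makes the middle column 0 throughout but leaves Day 29 open in the right-hand column. A floor of study Day 30 makes both columns 0.

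**The case against.** The best case for leaving 5.3 alone is that the consequence is remote. It takes an early visit, then a vaccine not planned at entry, then a recorded AE by Day 28 in someone with no other unsolicited AE. The study is randomized and descriptive, with no formal hypotheses, so a small shift common to all arms is unlikely to alter candidate selection. Releasing participants once the Day 29 blood is drawn is coherent for immunogenicity. Section 8.4.8 lets the investigator attribute an event to another cause, so the treatment-related tables should be little affected. SAP Section 6.2.4 already counts non-study vaccinations within 28 days by group, and separately influenza or COVID-19 vaccines, so the extent would be visible.

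All of this stands as a limit on size. It does not close the gap: the counts show the exposure without preventing it, and no rule flags or sets aside an AE that follows such a vaccine.

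A reader might infer three stronger things that the documents do not support:
- **That the Day 29 titer is contaminated.** It is not, because the blood is collected at the visit whose completion ends the deferral.
- **That such a participant must leave the PP Set.** Section 6.7.3 makes this possible, not required. Table 9 turns on major deviations that affect the immune response, and a vaccine permitted by 5.3 and given after the draw is not plainly one.
- **That ordinary AEs after an early visit will reliably reach the 28-day tables.** The schedule and the call script conflict on this.

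**Conclusion.** The gap is real and follows from the text alone: 5.3 permits an unplanned vaccine on Days 22–28, inside the primary unsolicited-AE period and inside the 28-day interval of 6.7.3. No other provision prohibits it.

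The exposed interval is at most 7 days per participant within the AE period, and zero for anyone seen on Day 29 or later. No number of affected participants is claimed, since visit timing and uptake are not given and criterion 11 already removes people with a vaccine planned. The effect is probably small. It is also probably not differential, which rests on randomization and on the same deferral rule applying in every arm. Confidence is high in the wording gap and lower in any visible effect on the tables, given the uncertain capture. This is a minor improvement, justified by its low cost.

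**What to change.** Amend Protocol Section 5.3 so that licensed or authorized vaccines are deferred until after completion of the Day 29 Visit and until more than 28 days after the study injection (study Day 30 or later), whichever is later.

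Keeping the visit condition protects a late blood draw. A Day 29 floor would be enough for the Day 1–28 AE period. Day 30 is needed to clear the 28-day interval in 6.7.3 when it is counted in elapsed days.

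The cost is one sentence, with no new procedure, table or data collection: non-study vaccinations are already recorded through Day 181 and listed. The extra wait is max(0, 30 − d) days for a visit on day d: up to 8 days for a Day 22 visit, falling to 1 day for a Day 29 visit and 0 from Day 30.
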